4 STUDY OBJECTIVES

4.1 Primary Objectives

- To evaluate the effect of weekly subcutaneous (SC) administration of abatacept on complete remission of IgG4-RD at 24 weeks

4.2 Secondary Objectives

- To evaluate the effect of abatacept on disease response at 4, 12 and 24 weeks and complete remission at 36 weeks
- To evaluate the effect of abatacept on time to disease remission (IgG4-RD RI = 0), remission rates, number of disease flares per subject over time
- To evaluate the effect of abatacept on physician global assessment (PGA), Symptom Severity Index, and cumulative corticosteroid doses
- To evaluate the effect of abatacept on serum immunoglobulin levels, IgG4 subclass concentrations, IgE levels, eosinophils, and serum C3 and C4 levels at 4, 12, 24 and 36 weeks

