All subjects completing the treatment period will have follow up visits off protocolized treatment at 28 and 36 weeks. All AE(s) (including serious AEs and deaths) and use of concomitant medication information will be collected throughout the study from screening through study termination. Subjects developing treatment-emergent AEs or clinically significant safety lab abnormalities will be followed until resolution or until stabilization of the AEs/abnormalities.

Signs and symptoms of IgG4-RD activity will be measured periodically throughout the study using a modification of the IgG4-RD RI ([Carruthers et al. 2012](#), [Wallace et al. 2016](#)). The IgG4-RD RI is based on the Birmingham Vasculitis Activity Score for Wegener's Granulomatosis ([Stone et al. 2001](#)) utilized for the evaluation and licensure of rituximab in ANCA-associated vasculitis ([Stone et al. 2010](#)). The IgG4-RD RI is an instrument designed to detect change in disease activity and identify improvements and worsening in the same or

different organ systems and has been used in prior clinical trials to monitor IgG4-RD disease activity ([Khosroshahi et al 2010](#), [Carruthers et al 2015](#), [Stone et al 2016](#)).

Assessments will include AE assessment, physical examination, vital signs, clinical laboratory testing (clinical chemistry, hematology, serum immunoglobulins, serum IgG4 subclasses, complements, and urinalysis) and concomitant medications. Additional serologic indicators of response will include immunoglobulin levels, IgG4 subclasses, IgE, Eosinophil levels, C3 and C4 levels.

Additional mechanistic studies will be conducted through the MGH NIH-funded Autoimmunity Center of Excellence for IgG4-RD, which has established translational collaborations between the MGH Clinic and the Ragon Institute of Harvard, MGH, and MIT (the laboratory of [name]).

Briefly, peripheral blood mononuclear cells (PBMCs) and plasma will be isolated and frozen from each subject at weeks 0, 1, 4, 12 and 24 corresponding with clinical blood draws. PBMCs and plasma will be stored in liquid nitrogen for preservation. The following experiments will be carried out in batches of 10 patient time points per experiment:

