5.1 Schedule of Assessments

The schedule of assessments is presented in table format in the study synopsis

Study Phase	Screening	Treatment														
		1	2	3	4	5	6	7	8	9	10	11	12	13	14	15
VISIT NUMBER	0	1	2	3	4	5	6	7	8	9	10	11	12	13	14	15
WEEK	0	1	2	3	4	5	6	7	8	9	10	11	12	13	14	15
Informed consent	X	X														
Study drug		X	X	X	X	X	X	X	X	X	X	X	X	X	X	X
Study drug Instruction		X														
Medical history ²	X ²	X ²			X ²				X ²				X ²			
Physical examination ³	X ³	X ³			X ³				X ³				X ³			
Adverse Event		X			X				X				X			
Record concomitant medications ⁴	X	X			X				X				X			
Vital signs ⁵	X	X			X				X				X			
CBC w/ differential, platelet count	X	X			X				X				X			
Comprehensive Metabolic Panel (CMP)	X	X			X				X				X			
Urinalysis and Urine protein/creatinine	X	X														
Urine Pregnancy test ⁷	X	X			X				X				X			
HBsAg, HBcAb, HCV**Not required if collected 6 months prior to screening	X															
Serum immunoglobulin levels (IgM, IgE, IgG)	X	X														
Serum IgG subclasses	X	X			X				X				X			
C3 and C4	X															
Mechanistic samples	X	X			X								X			
Fasting lipid profile	X	X			X				X				X			
CT chest, abdomen, pelvis ⁸	X															
IgG4-RD RI	X	X			X				X				X			
Physician Global Activity VAS	X	X			X				X				X			
Symptom Severity Index	X	X			X				X				X			
Glucocorticoid Toxicity Index	X	X			X				X				X			
SF-36 Health Survey	X	X			X				X				X			

Study Phase											
VISIT NUMBER	6				7				8	9	10/EO
WEE	16	17	18	19	20	21	22	23	24	28	36
Informed consent											
Study drug administration	X	X	X	X	X	X	X	X	X		
Medical history ²	X				X ²				X	X ²	X ²
Physical examination ³	X				X ³				X	X ³	X ³
Adverse Event assessment ⁴	X				X				X	X	X
Record concomitant medications ⁴	X				X				X	X	X
Vital signs ⁵	X				X				X	X	X
CBC w/ differential, platelet	X				X				X	X	X
Chemistry Panel	X				X				X	X	X
Urinalysis and Urine protein/creatinine											X
Urine Pregnancy test ⁷	X				X				X	X	X
HBsAg, HBcAb, HCV ^o											
Serum immunoglobulin levels (IgM, IgE, IgG)									X		X
IgG subclasses	X				X				X		X
C3 and C4											X
Fasting lipid profile	X				X				X		X
Mechanistic samples									X		
IgG4-RD RI	X				X				X		X
Physician Global Activity VAS	X				X				X		X
Symptom Severity Index	X				X				X		X
Glucocorticoid Toxicity Index	X				X				X		X
SF-36 Health Survey	X				X				X		X

¹The Screening visit (Visit 1) and the Treatment Week 1 (Visit 2) visit could potentially be on the same day

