5.2 Study Assessments

Screening Visit

The following procedures will be performed:

1. Obtain written informed consent after consent presentation
2. Obtain Medical history
 - a) Including demographics
 - b) Including history of IgG4-RD
3. Physical examination
4. Record concomitant medication
5. Vital signs including; BP, P, R, T, weight, and height.
 - a. Weight will be measured with outerwear and shoes removed
 - b. Height will be measured with shoes removed (screening visit only)
 - c. Blood pressure and pulse rate obtained after the subject has been supine ≥ 5 minutes
6. Adverse Event monitoring (from time of study drug administration)
7. Laboratory tests:
 - a. CBC with cell differential and platelets
 - b. Chemistry panel
 - c. Urinalysis and urine protein/creatinine ratio
 - d. Urine pregnancy test (only for woman of child bearing age)
 - e. Hepatitis B and C tests (not required if collected 30 days prior to screening visit)
 - f. Serum Immunoglobulin levels (IgM, IgE, IgG)
 - g. Serum IgG4 subclasses
 - h. Complement levels
 - i. Fasting lipid profile
 - j. Mechanistic samples will be collected from subject at weeks 0, 1, 4, 12 and 24 studies)
8. Imaging tests: CT chest, abdomen, pelvis
9. Physician reported outcomes
 - a. IgG4 Responder Index (IgG4-RD RI)
 - b. Physician Global Activity VAS
10. Patient reported outcomes
 - a. Symptom Severity Index
 - b. Glucocorticoid Toxicity Index
 - c. SF-36 Health Survey
 - d. Patient Global Activity VAS

Baseline Visit: Visit 2 (week 1)

The screening (visit 1) and baseline visit (visit 2) could potentially be combined and completed on the same day

The following procedures will be performed:

1. Verify eligibility criteria.
2. Review general medical and IgG4 history
3. Brief physical examination
4. Record concomitant medication
5. Vital signs including; BP, P, R, T, weight, and height.

- a. Weight will be measured with outerwear and shoes removed
- b. Blood pressure and pulse rate obtained after the subject has been supine ≥ 5 minutes
6. Adverse Event monitoring
7. Laboratory tests:
 - a. CBC with cell differential and platelets
 - b. Chemistry panel
 - c. Urinalysis and urine protein/creatinine ratio
 - d. Urine pregnancy test (only for woman of child bearing age)
 - e. Serum Immunoglobulin levels (IgM, IgE, IgG)
 - f. Serum IgG4 subclasses
 - g. Fasting lipid profile
 - h. Mechanistic samples will be collected from subject at weeks 0, 1, 4, 12 and 24 studies)
8. Patient-reported outcomes:

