5.6 Withdrawal of Subjects

Subjects are encouraged to complete all study evaluations. However, they may withdraw from the study at any time and for any reason. Every effort will be made to determine why any subject withdraws from the study prematurely. All subjects who withdraw from the study with an ongoing AE must be followed until the event is resolved or deemed stable. At the time that a subject withdraws prematurely for any reason, all assessments as listed for the EOS visit should be performed. If a subject withdraws prematurely after dosing, all data to be collected prior to discharge from the clinical site will be collected at the time of premature discontinuation or at the scheduled end-of-study visit. Subject participation may be terminated prior to completing the study and the reason recorded as follows:

1. Adverse event
2. Protocol violation

3. Loss to Follow-up
4. Subject withdrew consent
5. Investigator withdrew subject to give rescue therapy other than steroids
6. Other

A comprehensive effort must be made to determine the reason(s) why a subject fails to return for the necessary visits or is discontinued from the study. If the subject is unreachable by telephone, a registered letter, at minimum, should be sent to the subject requesting him/her to contact the study site.

Subjects withdrawn due to AEs considered to have a possible relationship to study drug will not be replaced. Subjects withdrawn for a non-drug related reason will be replaced if deemed necessary by the Sponsor. The decision regarding the replacement of subjects will be documented.

If a subject withdraws prematurely, all assessments as listed for the EOS visit should be performed and recorded on an unscheduled visit eCRF page. In addition, the subject should be scheduled for a follow-up visit 4 weeks from the time of the last injection of study drug, at which time all assessments as listed for the EOS visit should be performed.

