The following laboratory variables will be determined as outlined below:

Hematology: The following hematology parameters will be assessed: hemoglobin, hematocrit, red blood cell count, white blood cell count with differential (% and derived absolute values), mean corpuscular volume, mean corpuscular hemoglobin, mean corpuscular hemoglobin concentration, and absolute platelet count.

Clinical comprehensive metabolic test (CMP): The following clinical chemistry parameters will be assessed per schedule of assessment: Total protein, sodium, potassium, calcium, chloride, bicarbonate (HCO₃), albumin, glucose, blood urea nitrogen (BUN), creatinine, total bilirubin, alkaline phosphatase (AP), aspartate aminotransferase (AST), alanine aminotransferase (ALT), and hemoglobin A1C. Hemoglobin A1C will be used as a surrogate for pancreatic endocrine function. A fasting lipid panel and HbA1c will be performed during the GTI assessment visits.

Immunoglobulin: Serum IgM, IgG, and IgE will be assessed per schedule of assessment. Serum IgG subclasses will be measured per schedule of assessment

Complement levels: C3 and C4 levels will be assessed per schedule of assessment

Urinalysis and Urine protein/creatinine ratio: The following urinalysis parameters will be assessed per schedule of assessment: pH, glucose, ketones, specific gravity, nitrite, protein, bilirubin, urobilinogen, leukocytes and blood. Microscopic urinalysis will be performed if clinically indicated.

Serology: HBsAg, HBcAb, and HCV Ab will be performed at Screening. Not required if collected 6 months prior to screening visit.

Urine Pregnancy Test: Urine pregnancy testing will be performed in female subjects of childbearing age (if not surgically sterilized)

Mechanistic samples: Correlative Studies

Peripheral blood mononuclear cells (PBMCs) and plasma will be isolated and frozen from each subject at weeks 0, 1, 4, 12 and 24 corresponding with clinical blood draws. Flow cytometry looking at T cells will be assessed at weeks 0, 1, 4, 12 and 24. From 5 of the enrolled subjects

with known expansions of the respective cell type and clinical responsiveness to abatacept, terminally differentiated CD4+CTLs, terminally differentiated CD8+CTLs and activated B cells will be sorted by FACS at weeks 0, 12 and 24.

Blood Requirements:

Blood will be collected for clinical laboratory testing as outlined below:

Hematology: Blood (3 mL) will be collected into a lavender-top (EDTA) tube.

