Chemistry: Blood (5.0 mL) will be collected into a serum gel (SST) tube.

Hepatitis serologies (HBsAg, HBcAb, HCVAb): Blood (4.0 mL) will be collected into a serum gel (SST) tube. Immunoglobulins (IgG, IgM, IgE, IgG4) and Complement C3 and C4: Blood (5 mL) will be collected into a serum gel (SST) tube.

Flow Cytometry B Cell and CD19 RO: Blood (3.0 mL) will be collected into a lavender-top tube and blood (5.0 mL) will be collected in a Cyto-Chex BCT glass streck CE marked tube.

Plasmablast and CD4+ CTL Assessment: Blood (5.0 mL) will be collected in a Cyto-Chex BCT glass streck CE marked tube.

Laboratory Values Outside Normal Range:

Any value outside the normal range will be flagged for the attention of the Investigator or designee at the site. The Investigator or designee will indicate whether or not the value is of clinical significance. Laboratory values that are clinically significant and that are not explained by the subject's underlying disease or medications should be entered as AEs and the relationship to study drug assigned. A laboratory value of clinical significance typically requires a diagnostic or therapeutic intervention other than repeating the test. Additional testing during the study may be done if medically indicated. The study subject will be followed until the test(s) has (have) normalized or stabilized.

Physical Examination

Complete physical examinations will be performed at Screening, on Day 1 (could potentially be the same visit) and at EOS. Abbreviated PEs will be directed towards the symptoms of IgG4-RD that were previously defined and will be performed at all other visits.

The physical examination includes an assessment of general appearance and a review of systems (dermatologic, head, eyes, ears, nose, mouth/throat/neck, thyroid, lymph nodes, respiratory, cardiovascular, gastrointestinal, extremities, musculoskeletal, neurologic, and psychiatric systems).

Vital Signs

Vital signs will be assessed at Screening (Visit 1) and at each visit to the PI's office. The following vital signs will be measured:

- Blood pressure (systolic and diastolic [mmHg]);
- Heart rate (beats per minute [bpm]);
- Body temperature (°C);
- Respiratory rate (breaths per minute).

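### The serology objective names weeks 4, 12, 24 and 36, but the schedule collects no C3/C4 at weeks 4, 12 and 24 and no IgM/IgE/IgG at weeks 4 and 12

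*Protocol*

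**What the plan says.** Section 4.2 of the protocol includes a secondary objective that covers these measures: "serum immunoglobulin levels, IgG4 subclass concentrations, IgE levels, eosinophils, and serum C3 and C4 levels at 4, 12, 24 and 36 weeks". The secondary objectives in the synopsis give the same list with the same four weeks. The study description in section 5 gives these analytes a role beyond routine safety: "Additional serologic indicators of response will include immunoglobulin levels, IgG4 subclasses, IgE, Eosinophil levels, C3 and C4 levels".

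The Schedule of Assessments (section 5.1) has a separate row for each panel:

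- C3 and C4: screening (week 0) and week 36.
- IgM, IgE and IgG: weeks 0, 1, 24 and 36.
- IgG subclasses: weeks 0, 1, 4, 8, 12, 16, 20, 24 and 36.
- CBC with differential, which supplies eosinophils: the same weeks as IgG subclasses, plus week 28.

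The laboratory text within section 7.3 sets no timing of its own: "Complement levels: C3 and C4 levels will be assessed per schedule of assessment" and "Serum IgM, IgG, and IgE will be assessed per schedule of assessment". For the visits from week 4 to week 36, section 5.2 also refers laboratory tests to the schedule.

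**The concern.** The objective and the schedule cannot both be followed. A site working to the schedule will not draw complement at weeks 4, 12 or 24, or IgM, IgE and total IgG at weeks 4 and 12.

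Complement is affected most. In a completer, the two scheduled values fall either side of the whole treatment period, and the second comes 12 weeks after the last dose. A fall or rise during treatment that reverses afterwards would not be seen. IgM, IgE and total IgG have one later on-treatment value, at week 24, so the early course between weeks 1 and 24 is lost.

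This is a data-collection matter and cannot be left to the analysis plan. The study has no control group and enrols about 10 subjects, so within-subject change over time is the evidence these measures can offer.

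**Working it through.** No sample-size or error-rate figure is involved. The check compares the weeks the objective requires with the weeks the schedule marks.

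**Inputs.** Required weeks {4, 12, 24, 36}, from section 4.2 and the synopsis. Scheduled weeks, from the section 5.1 rows read column by column against the week headers (0 to 15, then 16 to 24, 28 and 36). Treatment weeks 1 to 24, from the study-drug row.

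| Analyte group | Weeks scheduled | Required weeks covered | Missing |
|---|---|---|---|
| C3/C4 | 0, 36 | 1 of 4 | 4, 12, 24 |
| IgM/IgE/IgG | 0, 1, 24, 36 | 2 of 4 | 4, 12 |
| IgG subclasses | 0, 1, 4, 8, 12, 16, 20, 24, 36 | 4 of 4 | none |
| Eosinophils (CBC differential) | 0, 1, 4, 8, 12, 16, 20, 24, 28, 36 | 4 of 4 | none |

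**Size of the gap.**

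- By group: 3 + 2 + 0 + 0 = 5 missing of 4 × 4 = 16 time points per subject, or 31%. For 10 completers this is 50 of 160.
- On treatment (weeks 4, 12 and 24): all 5 gaps fall here, so 5 of 4 × 3 = 12 are missing. C3/C4 has 0 of 3 and IgM/IgE/IgG has 1 of 3.
- By single measure (IgM, IgE, IgG, subclasses, eosinophils, C3, C4): 2 × 3 + 3 × 2 = 12 missing of 7 × 4 = 28, or 43%.

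**Could the table be damaged?** Each row has its full 16 and 11 columns. The CBC, IgG-subclass and study-drug rows, used as alignment checks, fall on the expected weeks. The visit lists in section 5.2 agree where they apply: the screening list includes "h. Complement levels" and the baseline list does not, while immunoglobulins appear in both. Those lists cover only screening and baseline, so for the disputed weeks the evidence is the row alignment.

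**Does anything else supply the missing weeks?** No. The schedule footnotes add no complement or immunoglobulin draws. The blood-requirements text gives tube volumes only. Section 5 names the analytes without weeks. Section 5.6 does produce values for early leavers: "At the time that a subject withdraws prematurely for any reason, all assessments as listed for the EOS visit should be performed". It also asks for the same assessments 4 weeks after the last injection. Those assessments include C3/C4 and IgM/IgE/IgG, but they come only from subjects who leave early and do not fill weeks 4, 12 and 24 for completers.

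**The case against.** Several points can fairly be made on the other side.

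- **The endpoints can still be reported.** The endpoint lists in the synopsis and section 8.2 name these measures without weeks, so they can be summarised from the scheduled draws. This is true, but the objective names the weeks and remains unmet.
- **Specimens exist.** Plasma is to be frozen at weeks 0, 1, 4, 12 and 24, which include the weeks in question. However, the protocol plans no complement, IgM, IgE or total IgG assay on it, and the blood-requirements text specifies serum tubes for these tests. Frozen plasma is at most a possible rescue.
- **It may be a drafting slip in the table.** The synopsis says immunoglobulins and complements are recorded regularly during the study, which suggests that more marks were intended. That would explain the mismatch, but sites would still follow the schedule as written.
- **The 31% depends on how the analytes are grouped.** This stands: counting single measures gives 43%. The firm facts are 1 of 4 for C3/C4 and 2 of 4 for IgM/IgE/IgG.
- **The consequence is limited.** This also stands. The protocol states no test, threshold or decision rule for these measures, and IgG subclasses and eosinophils are fully covered.

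**Conclusion.** The contradiction is real. The schedule leaves out C3/C4 at three of the four weeks the objective names and IgM/IgE/IgG at two of four. All five gaps fall during treatment. Subjects who complete the study as scheduled have no on-treatment complement value, so that part of the objective cannot be reported at weeks 4, 12 and 24.

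This rests on the schedule rows being read in correct alignment, which the neighbouring rows support, and it is limited to completers. The counts for 10 subjects assume that all 10 complete, whereas the protocol plans approximately 10. The point should be corrected, but it touches secondary descriptive measures only and leaves the primary endpoint unaffected.

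**What to change.** Mark C3/C4 at weeks 4, 12 and 24 and IgM/IgE/IgG at weeks 4 and 12 in the section 5.1 schedule. The blood-requirements text puts IgG, IgM, IgE, IgG4, C3 and C4 in one 5 mL serum tube, and IgG subclasses are already scheduled at weeks 4, 12 and 24. If the subclass test uses that tube, no extra draw or tube is needed. The added work for 10 completers is 2 × 3 × 10 = 60 complement assays plus 3 × 2 × 10 = 60 immunoglobulin assays, 120 in all.

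The alternative is to restate the objective in section 4.2 and the synopsis to the weeks collected: C3/C4 at week 36 against screening, and IgM/IgE/IgG at weeks 24 and 36. This costs nothing but gives up on-treatment complement data.

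Two timing points can be tidied in the same amendment:

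- State whether week 1 is the first-dose baseline visit, as in sections 5.1 and 5.2, or a later visit, as section 6.3 implies. This decides whether week-1 samples, including the mechanistic sample, are taken before or after treatment starts. The clarification is free if week 1 is the first-dose visit. A post-dose week-1 sample would need a draw that is not now scheduled.
- Align the endpoint wording that the physician global assessment is collected at every visit with the schedule, which has no mark for it at week 28. This is editorial, since sections 5.2 and 7.2 already let the schedule govern.

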4.3 Exploratory Objectives

To evaluate the effect of abatacept on CD4+ T cells and B cell subsets, specifically:

- CD4+ cytotoxic T lymphocytes
- CD8+ cytotoxic T lymphocytes
- CD4+ T follicular helper cells
- CD4+ peripheral helper T cells
- Plasmablasts
- Activated B cells

5 INVESTIGATIONAL PLAN

Overall Study Design and Plan

Description

This is a Phase 2, prospective, open-label, single center clinical trial in subjects with active IgG4-RD. Approximately 10 subjects with active IgG4-RD will be enrolled. After screening and enrollment, eligible subjects will receive an initial subcutaneous dose of abatacept (125mg) followed by weekly subcutaneous doses of abatacept (125mg) for a total of up to 24 doses (24 weeks). Subjects will be followed on study for 12 weeks following the last dose for a total study period of up to 36 weeks.

After obtaining informed consent, all screening procedures and tests establishing eligibility will be performed on the initial screening visit. Subjects determined to be eligible at screening will receive an initial subcutaneous dose of abatacept (125mg), which will be continued weekly for a total of up to 24 doses (24 weeks). Steroid therapy must be tapered off and discontinued over a 4 week period (taper must be completed no later than week 4). Should patients be deemed to have worsening disease or failing therapy at 4 weeks then a trial of steroids can be considered.

Subjects will return on weeks 1, 2, 4, 8, 12, 16, 20, and 24 while on treatment for their injections, and for the scheduled safety and disease response assessments. Subjects will be allowed to self-administer their injections at home. The full treatment period is 24 doses given weekly for 24 weeks. Subjects who are not able to be tapered off corticosteroids or who require reinstitution of corticosteroid therapy at any time during the study will be counted as treatment failures but may continue on study. Should the IgG4-RD responder index fail to improve by 8 weeks or who develop new organ involvement by week 4 will be deemed a treatment failure, patient's will be deemed treatment failure and can begin corticosteroid or alternative immunosuppressive therapy at the Investigator's discretion. Those who require rituximab or who require addition of other oral immunosuppressive will be counted as treatment failures and will terminate the study.

All subjects completing the treatment period will have follow up visits off protocolized treatment at 28 and 36 weeks. All AE(s) (including serious AEs and deaths) and use of concomitant medication information will be collected throughout the study from screening through study termination. Subjects developing treatment-emergent AEs or clinically significant safety lab abnormalities will be followed until resolution or until stabilization of the AEs/abnormalities.

Signs and symptoms of IgG4-RD activity will be measured periodically throughout the study using a modification of the IgG4-RD RI ([Carruthers et al. 2012](#), [Wallace et al. 2016](#)). The IgG4-RD RI is based on the Birmingham Vasculitis Activity Score for Wegener's Granulomatosis ([Stone et al. 2001](#)) utilized for the evaluation and licensure of rituximab in ANCA-associated vasculitis ([Stone et al. 2010](#)). The IgG4-RD RI is an instrument designed to detect change in disease activity and identify improvements and worsening in the same or

different organ systems and has been used in prior clinical trials to monitor IgG4-RD disease activity ([Khosroshahi et al 2010](#), [Carruthers et al 2015](#), [Stone et al 2016](#)).

Assessments will include AE assessment, physical examination, vital signs, clinical laboratory testing (clinical chemistry, hematology, serum immunoglobulins, serum IgG4 subclasses, complements, and urinalysis) and concomitant medications. Additional serologic indicators of response will include immunoglobulin levels, IgG4 subclasses, IgE, Eosinophil levels, C3 and C4 levels.

Additional mechanistic studies will be conducted through the MGH NIH-funded Autoimmunity Center of Excellence for IgG4-RD, which has established translational collaborations between the MGH Clinic and the Ragon Institute of Harvard, MGH, and MIT (the laboratory of [name]).

Briefly, peripheral blood mononuclear cells (PBMCs) and plasma will be isolated and frozen from each subject at weeks 0, 1, 4, 12 and 24 corresponding with clinical blood draws. PBMCs and plasma will be stored in liquid nitrogen for preservation. The following experiments will be carried out in batches of 10 patient time points per experiment:

1. Flow cytometric quantification of plasmablasts, activated B cells, terminally differentiated CD4+ cytotoxic T cells (CD4+CTLs), terminally differentiated CD8+ cytotoxic T cells (CD8+CTLs), activated follicular helper T (TFH) cells and peripheral helper T (TPH) cells. Terminal differentiation will be defined by the loss of CD28 surface expression and gain of CD57 surface expression within the respective effector (CD45RA-CCR7-) T cell population. These cell populations will be assessed at weeks 0, 1, 4, 12 and 24 to determine the treatment effect on the absolute numbers and proportions of these cell types.
2. Quantified cell populations will be analyzed for correlation with one another, disease activity, plasma IgG4 levels and clinical responsiveness to abatacept.
3. From 5 of the enrolled subjects with known expansions of the respective cell type and clinical responsiveness to abatacept, terminally differentiated CD4+CTLs, terminally differentiated CD8+CTLs and activated B cells will be sorted by FACS at weeks 0, 12 and 24. RNA will be isolated to undergo RT-PCR amplification of the TCR- β /IgH, respectively. Next-Generation Sequencing will be used to define the diversity of the TCR/BCR repertoire longitudinally to ascertain how abatacept may impact clonality.

